## Study Summary

Title	Fundamental Virtual Reality Simulation for Manual Small Incision Cataract Surgery Validity: Evaluation, Efficacy and Acceptability Study in Bangladesh, China, Ethiopia, India, Mongolia, Togo, United Kingdom and United States of America.
Design	
Prospective Pre-Post single-masked education-intervention randomized controlled study of intense virtual reality (VR) simulation-based surgical education of ophthalmologists in Bangladesh, China, Ethiopia, India, Mongolia, Togo, UK and USA.
 
Construct validity study of assessment scores generated by the VR simulator for novices versus experts.
 
Qualitative study of face validity of VR simulator, and acceptability questionnaire survey of users.

Aims	To investigate the efficacy of intense VR simulation-based surgical education using the Orbis-FVR simulator. To examine whether it improves competence; is acceptable and has validity. To assess the construct validity of the VR simulator's assessment capacity.
Intervention	The 'intervention training' is a structured course of training using the Orbis-FVR MSICS simulator. This training is in addition to, and an enhancement of the trainees' normal current standard conventional training, and not designed to replace it.

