# Methodology

## Design Summary

This research program involves a prospective, single-masked education-intervention randomized controlled study of intense virtual reality (VR) simulation-based surgical education of ophthalmologists in Bangladesh, China, Ethiopia, India, Mongolia, Togo, UK and USA. Participants will be randomized, and simulation surgical competency will be assessed at baseline and 1-month between groups. Competency will be assessed at using artificial model eyes: both groups will perform three full MSICS cases using model eyes at baseline. At one-month post intervention, both groups will again perform three full MSICS using model eyes (primary outcome).

The study will assess the construct validity study of assessment scores generated by the VR simulator for novices versus experts. Both Novices and Experts will perform three full VR cases using the simulator. The first score will be disregarded to allow for familiarization with the hardware, and the mean of the second and third cases will be recorded.

Qualitative study of face validity of VR simulator, and acceptability questionnaire survey of users. An anonymous survey administered to experts and novices, using a Likert scale.

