## Outcomes

In the Fundamental Virtual Reality MSICS study, participants will be assessed on one occasion after recruitment (in addition to baseline), at one month: three simulation MSICS procedures recorded, anonymized and remotely assessed in a masked fashion (primary outcome). On the baseline and 1-month assessment, simulation MSICS procedures will be recorded (with masked assessment using the Sim-OSSCAR).

Primary Outcome – Orbis-FVR Study

**The primary outcome measure of the Orbis-FVR study will be the procedure specific repeated measures analysis of Sim-OSSCAR score performed three times at 1-month.** The analysis of the primary outcome measure will be based on the mean differences in the Sim-OSSCAR scores between the intervention and control groups. This score is derived from an assessment matrix or rubric of procedure specific and general microsurgical skill indices (see appendix 4). Each item in the matrix is graded on a modified Dreyfus score (novice, advanced beginner, and competent). The total possible score is 40 points.

Simulation assessment will be recorded using a standard microscope and recording device with all participants wearing similar latex-free surgical gloves. Recordings will be given an anonymous number to give no indication as to in which arm the surgeon is. Assessments of the surgical video will be conducted separately by two masked observers, watching the recorded surgery performed by the trainee at a separate time and place. Both observers are experienced eye surgeons and surgical trainers. Intra- and Inter-observer reliability studies will be conducted.

Secondary Outcomes / Qualitative Outcomes / Additional Exploratory Analysis:

1. Step-specific analysis: Secondary analysis of the primary outcome measure: mean differences in Sim-OSSCAR score for the seven interactive steps assessed (incision, tunnel, AC entry, CCC, mobilization, removal and IOL). Total possible score 14.
2. Assessment scores generated by Orbis-FundamentalVR MSICS simulator for two cohorts of surgeon: novice and expert (construct validity).
3. Self-reported confidence ratings (10-point Likert scale) in MSICS skills, and ophthalmic surgical skills.
4. Face validity assessment of Orbis-FVR simulator by international group of MSICS expert surgeons, performed through survey, using 5-point Likert scale.

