## Analysis

Statistical analysis

The primary outcome measure (mean Sim-OSSCAR score at 1 month) will be analyzed using a t-test. Performances will be compared between intervention and control groups: these are a continuous variable in each group. We will compare these mean Sim-OSSCAR^1 scores by t-tests (which is unadjusted) and linear regression (adjusting for training center as a fixed effect). An alpha level of  $p < 0.05$  will be considered statistically significant, and a kappa coefficient of  $\geq 0.75$  for inter-rater agreement is considered

excellent.

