## Sample size

Based on pilot and published data we anticipate the mean Sim-OSSCAR score to be 10/40 (standard deviation (SD) 6 points) at baseline. We anticipate an effect size of 2.5 SD in the mean Sim-OSSCAR between groups. We assume a correlation between these observations of 0.8. Variation between clusters (training institutions) will be accounted for with a co-efficient of variation of 0.5.

Therefore, a sample of 52 individuals in total (26 in each arm) would have 80% power and 95% confidence to detect a difference of 15 points (2.5SD). We will recruit 60 participants for the Orbis-FVR training study to provide 8 extra participants as we anticipate a moderate loss to follow-up.

We and our collaborators consider this sample size of 60 participants to be feasible within the available time and financial resources. It would take longer (an extra academic year) if we needed to recruit many more, and if the impact of COVID-19 on training continued throughout the recruitment year.

For the construct validity of the FVR assessment capacity, we will recruit a total of 5 experts and 5 novices from participating centers. Sample sizes of content, face and construct validity study are based on data from recent validation studies of ophthalmic simulation surgical competency assessment rubrics. Additionally, as we predict a large differences between the two participating groups, small cohort numbers suffice. For face validity, we will recruit ten experts from multiple centers, likewise, this was determined based on data from similar face validation studies.

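### The masked baseline Sim-OSSCAR score is collected in both arms but enters neither planned primary comparison, which may give up precision (0% to 39% of the confidence-interval half-width)

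*Combined protocol and SAP*

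**What the plan says.** The Design Summary states that "both groups will perform three full MSICS cases using model eyes at baseline", and the Outcomes section adds: "On the baseline and 1-month assessment, simulation MSICS procedures will be recorded (with masked assessment using the Sim-OSSCAR". Each participant should therefore have a masked baseline score on the outcome scale.

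The Analysis section compares the mean 1-month score between arms by an unadjusted t-test and by a "linear regression (adjusting for training center as a fixed effect". No baseline term is named. The Outcomes section does call the primary outcome a repeated measures analysis, but the repeats are the three cases at 1 month.

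Two places suggest that baseline may have been meant to play a part. The Study Summary calls the trial a "Prospective Pre-Post single-masked education-intervention randomized controlled study". The Sample size section says "we anticipate the mean Sim-OSSCAR score to be 10/40 (standard deviation (SD) 6 points) at baseline", gives the anticipated effect, and then says "We assume a correlation between these observations of 0.8" without identifying the observations. It continues: "Variation between clusters (training institutions) will be accounted for with a co-efficient of variation of 0.5".

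**The concern.** A baseline measurement of the outcome is often the strongest available predictor of the final score. Leaving it out of a randomised comparison does not bias the result, but it can leave the interval wider than the data allow. With 26 per arm and SD 6, the baseline difference between arms has a standard error of 6 × √(2/26) = 1.66 points, so a chance gap of up to about 1.96 × 1.66 = 3.3 points would be unremarkable. If the analysis model does not already contain baseline, any later adjustment for such a gap is post hoc.

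The size of the effect is used in two places. The Cost-effectiveness section puts the score difference in the denominator of its ratio, and the Executive Summary says the results will inform a future trial. Both uses are modest: Risks and Limitations says live surgical competence is not assessed, and nothing in the documents shows that a narrower interval would change a decision.

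**Working it through.** **The plan's own figure.** The sample size is 26 per arm for 15 points, SD 6, 80% power. The plain two-group formula gives 2 × (1.96 + 0.84)² × 6² / 15² = 2.5, so 3 per arm (4 with the exact t calculation). Treating 0.8 as a baseline-to-outcome correlation multiplies this by 1 − 0.8² = 0.36, giving 1 per arm. No variant tried for this individually randomised design gives 26, so the meaning of the 0.8 cannot be recovered by working back from the sample size.

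**Inputs.** From the documents: 52 analysed, 1:1 (Sample size); 9 centres (Study Setting; the Randomisation section says ten); SD 6 (Sample size, baseline only). Assumed: SD 6 within centre also at 1 month in both arms; two-sided 95% intervals; within-centre baseline-to-1-month correlation r, varied.

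**Formula.** The centre-adjusted regression has 52 − 9 − 1 = 42 residual degrees of freedom, and 41 with baseline added.

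- Half-width without baseline: t(0.975, 42) × 6 × 2/√52 = 2.018 × 1.664 = 3.36 points.
- Ratio with to without baseline: √[(1 − r²) × (1 + 1/40)] × t(0.975, 41)/t(0.975, 42) = √[(1 − r²) × 1.025] × 1.0007.
- Break-even (ratio = 1): r = 0.16. Across 52 or 60 participants and 9 or 10 centres it runs from 0.146 to 0.163.

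**Results**, with a simulation (3,000 to 6,000 trials per case; eight centres of 6 and one of 4) as a check:

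| r | Change by formula | Simulated half-width, centre only → with baseline | Simulated change |
|---|---|---|---|
| 0 | +1.3% | 3.34 → 3.38 | +1.3% |
| 0.15 | +0.2% | 3.34 → 3.34 | +0.2% |
| 0.2 | −0.7% | 3.34 → 3.31 | −0.8% |
| 0.3 | −3.4% | 3.33 → 3.22 | −3.4% |
| 0.5 | −12.3% | 3.34 → 2.93 | −12.3% |
| 0.8 | −39.2% | 3.33 → 2.03 | −39.1% |

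The percentages do not depend on the SD, but the points do. At r = 0.8 the half-width goes from 2.22 to 1.35 with SD 4, and from 4.46 to 2.70 with SD 8. With ten centres the percentages agree to within 0.2 percentage points.

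**Another reading of the 0.8.** Suppose 0.8 is the overall correlation, SD 6 is the total SD, centre means are stable over time, and the coefficient of variation of 0.5 applies to the mean of 10. The between-centre SD is then 5, the within-centre variance is 36 − 25 = 11, and the within-centre r is (0.8 × 36 − 25)/11 = 0.345. Simulated half-widths are 3.20 (t-test), 1.84 (centre) and 1.75 (centre plus baseline). Centre adjustment already brings most of the gain here, and baseline adds 4.9%.

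**Unequal correlation.** With r = 0.8 in the control arm and 0.3 in the intervention arm, the gain is 15.5%.

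**If baseline is affected by allocation.** Suppose learning given only to the intervention arm raises its baseline. With equal SDs at the two times, the adjusted estimate is then too low by r × rise. For an assumed 2-point rise this is 0.3 (r = 0.15), 0.6 (0.3), 1.0 (0.5) or 1.6 points (0.8). Simulated estimates of a true 15 points were 14.77, 14.39, 14.02 and 13.37. The t-test and centre-adjusted estimates stayed at 15.0 to 15.1.

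**Power.** The t-test with 26 per arm has power above 99.99% for 15 points at SD 4, 6 or 8. At SD 6, 80% power is reached at 2.80 × 1.664 = 4.7 points.

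**The case against.** The case for leaving the plan alone has four parts.

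- **No decision depends on it.** The planned analyses are valid, power at 15 points is ample, and no interval is planned for the cost-effectiveness ratio. This stands, and it is why the point ranks only as an improvement. Precision would matter more if the true effect were far below 15 points.
- **The 39% is the top of an assumed range.** It needs 0.8 to be the within-centre correlation of baseline with 1 month in both arms. The plan does not say so; the 0.8 could equally link the repeated cases. Eligibility is limited to trainees with no MSICS as primary surgeon and fewer than 10 assisted, which may narrow the baseline spread. Training one arm to a score threshold may also loosen its link with starting skill. All of this stands.
- **Adjustment carries a timing risk that the current plan does not.** The Design Summary says "Participants will be randomized, and simulation surgical competency will be assessed at baseline and 1-month between groups", naming randomisation first. Table 2 lists a surgical video review a month ahead and the baseline recordings a week ahead, under the training-program heading. At r = 0.5, standard errors of 1.66 (centre only) and 1.46 (with baseline) mean that an arm-specific rise of about √(1.66² − 1.46²)/0.5 = 1.6 points would cancel the gain in mean squared error. This stands as a condition. It is eased, but not removed, by the Course outline, which asks for confirmation of the three uploads before the intervention. That places baseline ahead of the course but not ahead of allocation.
- **The change is not wholly free.** Sites must confirm the order of events. This also stands.

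None of these points supplies a baseline term that the Analysis section lacks, and the worst loss from adding one, if the order holds, is about 1% of the half-width.

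**Conclusion.** The concern holds. The baseline Sim-OSSCAR score is collected, masked and on the outcome scale, and no section brings it into the primary comparison. The consequence is a possible loss of precision, with no bias and no effect on power for the planned difference. With 52 analysed in 9 centres, the half-width that could be saved runs from nothing at a within-centre correlation of about 0.15 to 39% at 0.8. At SD 6 the latter is 3.3 down to 2.0 points. Below break-even the cost is at most about 1%.

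The omission and the arithmetic are firm; the actual gain is not, because the plan never says what its 0.8 refers to. Adjustment is safe only if baseline is recorded before allocation is revealed and before any learning given to one arm only.

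**What to change.** 1. In the Analysis section, make the primary analysis a linear regression of each participant's mean 1-month Sim-OSSCAR score on arm, training centre and mean baseline Sim-OSSCAR score. Keep the t-test as supportive.
2. Keep participants with a missing baseline score by a simple imputation that ignores arm, for example the centre's mean baseline score.
3. State in the Design Summary and Table 2 that all three baseline cases are recorded before allocation is revealed and before any learning given to one arm only.
4. If that order cannot be guaranteed at every site, keep the centre-adjusted regression without baseline. Settle this before recruitment.
5. In the Sample size section, say which observations the 0.8 refers to.

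The cost is a few sentences and one degree of freedom, with no new measurement. Setting or confirming the order of baseline recording, allocation and pre-learning at each site is a real operational task.

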### Qualitative analysis

Structured anonymous survey (appendix 8), using a 5-point Likert scale, to assess acceptability of VR simulator by Novice and Expert study participants.

Face validity assessment of Orbis-FVR simulator by international group of MSICS expert surgeons, performed through survey, using 5-point Likert scale.

### Cost-effectiveness

Cost effectiveness will be evaluated by calculating the incremental cost-effectiveness ratio (for the primary outcome of Sim-OSSCAR scores of surgical competency:

ICER = cost of Orbis-FVR Simulation module per group of trainees divided by the difference in their outcomes (Scores).

Cost-effectiveness will also be assessed against the expense of the VR simulator and model eyes with trainers time, versus trainers time alone; and compared at different safety and learning curves for competency outcomes of participants per group.

Willingness-to-pay will be assessed as a crude monetary value per simulator, then per trainee outcome.

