## Executive Summary

Cataract is the leading cause of blindness, representing 35% of global blindness. There is a huge need to perform high volumes of cataract surgery globally, to tackle the backlog of cataract cases. There is a great need to train many eye surgeons safely, efficiently, effectively, and to an acceptable level of competence.

Currently, surgical training is often conducted using the traditional “apprentice model”, where a trainee observes a qualified surgeon and learns from them, and then the surgeon supervises the trainee performing surgery on a patient. We believe that this conventional model has substantial limitations and drawbacks, making surgical training less efficient and less safe. Simulation-based surgical education in cataract and glaucoma surgery has been shown to be effective in improving competence and confidence of trainee eye surgeons. However, the role of an immersive haptic virtual reality learning environment has not been established for manual small incision cataract surgery.

We will test the hypothesis that intense virtual reality (VR) simulation-based ophthalmic surgical training impacts initial acquisition of competence in key stages of MSICS. Orbis International has partnered with FundamentalVR and expert cataract surgeons to create a MSICS simulator, using virtual reality software combined with existing gaming technology. The result is a VR simulator available at a fraction of the cost of cataract surgical simulators currently on the market. We are proposing a pilot randomized multi-country study evaluating the efficacy and acceptability of the simulator training, using simulation alone. This mix method study will combine qualitative and quantitative data collection; no patients are involved.

All the training within the ‘educational intervention’ of this study will be performed using simulation. There is no testing or interventional surgical training on patients. When three anonymized and non-identifiable recordings of supervised cataract surgical procedures are video recorded (at one month), no patients are involved, and these assessments are, as for the baseline assessments, using validated artificial model eyes and assessment rubric.

The results of this study will inform the design of a future multi-center randomized-controlled clinical trial.

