## Appendix 6. Proposed Budget

Description	Unit cost (USD)	Quantity	Total (USD)
Research Project Costs			
Artificial eyes	250	60	15,000
Shipping for eyes	1	3000	3,000
Customs fees for eyes	14.7	30	441
AV/IT for video recording	5	100	5,000
Cost of grading (outsourced)	5	360	1,800
Course build out on CS	2,500	1	2,500
Cost for data analysis	1	5000	5,000
Publication costs	1	3000	3,000
Technical support	700	12	8,400
Research Project subtotal			44,141
Country Support Costs			
Country team support Bangladesh	8,460	1	8,460
Country team support Ethiopia	12,840	1	12,840
Country team off support India	8,063	1	8,063
Country office subtotal			29,363
VR Kit Shipping Costs			
Custom fees	3000	6	18,000
Shipping fees	TBD	7	15,000
Shipping Subtotal			33,000
TOTAL			106,504

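### The supplementary cost comparison charges model eyes to the VR side only, although both arms use them equally, and leaves trainer time undefined

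*Combined protocol and SAP*

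**What the plan says.** The Cost-effectiveness section under Analysis contains two comparisons. The first is a ratio: "ICER = cost of Orbis-FVR Simulation module per group of trainees divided by the difference in their outcomes (Scores"). The second is supplementary: "Cost-effectiveness will also be assessed against the expense of the VR simulator and model eyes with trainers time, versus trainers time alone". It states no denominator of its own and does not say what trainer time covers. It goes on to mention comparison over safety and learning curves for each group.

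The Study Summary describes the intervention as a "structured course of training using the Orbis-FVR MSICS simulator", given on top of usual training. Under Design Summary, "both groups will perform three full MSICS cases using model eyes at baseline", and at one month "both groups will again perform three full MSICS using model eyes (primary outcome"). The Executive Summary says of the one-month recordings that "these assessments are, as for the baseline assessments, using validated artificial model eyes and assessment rubric".

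Appendix 6 budgets "Artificial eyes 250 60 15,000" (unit cost, quantity and total in USD). Separate lines give USD 3,000 for shipping the eyes, USD 441 for customs, and 360 gradings at USD 5.

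**The concern.** An incremental cost should contain only what differs between the arms whose outcomes are being compared. The trial measures the VR course plus usual training against usual training. The second comparison adds an item that both arms consume equally, and it places an undefined item on both sides.

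Two things are at stake. Model-eye spending, which belongs to measuring the outcome, would be reported as a cost of VR training. Course mentoring, which is a real cost of VR training, could cancel out. Cost matters to the trial's rationale: the Executive Summary presents the simulator as much cheaper than its competitors. This sentence is also the only place in the section where cost components are named, because the module in the first formula is not itemised.

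**Working it through.** **1. Who uses the model eyes.** Design Summary gives each trainee in either arm 3 cases at baseline and 3 at one month, so 6 per trainee. Table 2 and Appendix 3 list three recorded model-eye cases as a pre-course assignment, which matches the baseline assessment. The rest of the course (Course Overview to Course outline) uses the simulator, videos and mentors. The grading budget is consistent with this: 60 trainees × 3 cases × 2 time points = 360. That is a consistency check, not proof, because Outcomes plans two observers per recording. The between-arm difference is 6 − 6 = 0 cases, so the incremental model-eye cost is zero.

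**2. The plan's own figure.** 250 × 60 = USD 15,000, as stated. With shipping and customs: 15,000 + 3,000 + 441 = USD 18,441.

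**3. Spurious cost if charged to one side.** Inputs are 60 recruits (Sample size), taken as 30 per arm; the 60 budgeted units serving the 60 trainees; and a planned difference of 15 points. Differences of 10 and 5 points are illustrative. The added cost per point is the added cost per VR trainee divided by the difference.

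| What is charged to the VR side | USD per VR trainee | Per point at 15 | at 10 | at 5 |
|---|---|---|---|---|
| Half the eyes (7,500/30) | 250 | 16.67 | 25.00 | 50.00 |
| Half, with shipping and customs (9,220.50/30) | 307.35 | 20.49 | 30.74 | 61.47 |
| All the eyes (15,000/30) | 500 | 33.33 | 50.00 | 100.00 |
| All, with shipping and customs (18,441/30) | 614.70 | 40.98 | 61.47 | 122.94 |

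**4. Trainer time.** Let K be the simulator and related course costs, E the model-eye cost placed on the VR side, M course mentoring and S usual supervision. Course Content and Course delivery describe local and international mentors for the VR course only. The training is an add-on, so S occurs in both arms. The correct increment is K + M.

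- Trainer time means course mentoring on both sides: (K + E + M) − M = K + E. The error is E − M.
- It means usual supervision on both sides: (K + E + S) − S = K + E. The error is again E − M.
- It means supervision plus mentoring on the VR side and supervision alone on the other: (K + E + S + M) − S = K + E + M. The error is E.

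E is wrongly included on every reading. M is lost on the first two. The documents give no figure for M, so the sign of E − M cannot be determined. It would turn negative once mentoring cost more than the USD 250 to 615 per trainee in step 3.

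**5. Learning curves and safety.** Course Overview has the simulator log attempts and adverse events during the course, which only the VR arm attends. The data shown to exist in both arms are the six Sim-OSSCAR cases per trainee.

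**The case against.** The strongest reply is that the sentence is supplementary. The leading formula divides module cost by score difference, names neither model eyes nor trainer time, and suits an add-on design. A reader might infer that the whole cost-effectiveness analysis is mismatched; the documents do not support that.

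A reader might also infer that the comparator does not exist in the trial. That follows only if trainer time means course mentoring. The Executive Summary describes conventional training as supervision by a surgeon, and read that way the comparator is the control condition. The fair criticism is that the term is undefined.

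Table 2 and Appendix 3 place three model-eye cases inside the description of the training programme, which may explain the wording. It does not rescue the costing, because Design Summary has both arms perform the baseline cases.

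It would also go too far to say that controls contribute nothing on learning or safety. They have six scored cases each, and the Appendix 4 rubric grades events such as radial tears and posterior capsule piercing.

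Finally, the share of total cost cannot be judged. No simulator price is given, and kit shipping and customs alone are budgeted at USD 33,000, or 33,000/30 = USD 1,100 per VR trainee. These limits stand and keep the point small. They leave the one-sided charge for model eyes in place.

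**Conclusion.** The second comparison is wrong as written on model eyes and ambiguous on trainer time. The model-eye error is the step 3 range, on the assumptions of 1:1 allocation with 30 per arm and the Appendix 6 prices. Its width reflects whether half or all of the eyes are charged and whether shipping and customs are included, neither of which the plan specifies.

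It is tempting to conclude that VR training will look less cost-effective than the trial shows. The documents do not support that as a net effect, because losing mentor time would push the other way and its cost is not given. The first formula and the primary analysis are not affected. Cost-effectiveness is the last entry in a combined list of secondary, qualitative and exploratory outcomes in a self-described pilot, so the severity is minor.

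**What to change.** Reword the second comparison so that costs are listed by arm:

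- Exclude model eyes and grading as assessment costs, or charge them equally to both arms.
- Define trainer time and name the comparator as usual training.
- Count simulator kit, kit shipping and customs, course build, and local and international mentor time as the incremental cost. The sponsor must supply the simulator price.
- Estimate mentor time from the course timetable or a simple log. The attendance items under Course outline are not shown to capture mentor hours.
- Report simulator-log learning curves and adverse events as descriptive for the VR arm, and confine any between-arm competency or safety comparison to the Sim-OSSCAR cases scored in both arms.

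The cost is a few sentences and a little extra costing work. No added participants, visits or assessments are needed.
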